#### 4.8 Enrollment Schedule Overview

This study will enroll participants in four cohorts with 12 participants in each cohort. Each subsequent cohort will receive a higher dose of study drug. Within each cohort, 9 individuals will receive active treatment and 3 will receive placebo.

Sentinel Dosing: For the first dose in each cohort, all subjects will be dosed in a sentinel manner. The sentinel dose will be administered in the following pattern:

- Initially two participants (1 with active treatment and 1 with placebo) will be dosed and monitored for an observational period covering twice the predicted tmax (48 hours).
- The Novo Nordisk Trial Safety Group and the TrialNet Medical Monitor will review data (as described section 4.9.1) from these two individuals. If approved by both, enrollment of the next three participants will occur (2 with active treatment and 1 with placebo). These three will then be dosed and monitored for 48 hours.
- The Novo Nordisk Trial Safety Group and the TrialNet Medical Monitor will review data (as described section 4.9.1) from these 3 individuals as well as any new data from the first two participants. If approved by both groups, enrollment of the remaining seven participants will occur (6 with active treatment and 1 with placebo).

Cohort Enrollment: Evaluation of accumulated data (as described section 4.9.2) will occur independently by the Novo Nordisk Trial Safety Group and the TrialNet Data Safety Monitoring Board when at least 9 individuals within a cohort have data available from visit 6. If approved by both, randomization of the next cohort will proceed.

Participants who are screened but are not included in the current cohort may rescreen for participation in a later cohort.

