#### 5.4 Metabolic Outcome Assessments

Metabolic assessments will consist of:

- · Glucose records and reports of hypoglycemia
- Insulin dose
- HbA1c
- MMTT: 2-hour MMTT at screening and at 1, 3, 6, and 12 months after initial treatment dose
- CGM data will be collected from participants who already use these devices as part of their clinical care

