#### 8.5 Statistical Considerations for Assessment of Worsening of Insulin Secretion.

Acceleration of beta cell destruction due to immune activation is a potential risk, which will be monitored through AUC0-2h,C-peptide,MMTT. The log-transformed area under the plasma C-peptide concentration-time curve from time 0 to 2 hours during MMTT obtained at the end-of dosing day 84 for the treatment and placebo arms will be compared for each cohort (N=3 placebo, and N=9 treated) and at the end of the study by cohort (i.e., pooling the placebo treated patients, N=12 placebo, N=9 treated in each cohort). The study has a 72%-87% power to detect a 50% or less treatment ratio when the coefficient of variation (CoV) ranges from 0.38 to 0.31. This is based upon historical data derived from recent onset patients (51). Should the observed CoV be larger, there would be a corresponding reduction in power to detect a 50% treatment ratio or a corresponding decrease in the detectable treatment ratio to retain 80% or greater power. The power to detect a 50% or less treatment ratio at the end of the study (using the pooled placebo patients) is uniformly >90%.

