6.2 SECONDARY ENDPOINTS

 $\Delta AUC_{0-2h,C-peptide,MMTT}$; Relative change in the area under the plasma C-peptide concentration-time curve from time 0 to 2 hours during MMTT from baseline to 3 months (visit 14) between groups. The comparison will be blinded until the last patient has been followed for 12 months.

Additional Outcomes and Analyses

It is the aim to perform additional analysis to get information of the appearance and disappearance of Plasmid DNA and RNA at various time points during the trials conduct period:

- Plasmid DNA and RNA concentrations at selected time points before and from 1 hour to up to 48 hours after the first dose (Visits 0-2, days 0-2)
- Plasmid DNA and RNA concentrations before second dose (Visit 3, day 7 +/- 1 day)
- Plasmid DNA and RNA concentrations before dose 5 (Visit 6, day 28 +/- 1 day)
- Plasmid DNA and RNA concentrations before dose 8 (Visit 9, day 49 +/- 1 day)

• Plasmid DNA and RNA concentrations at selected time points after last dose (Visit 14, day 84 +/- 3 days; Visit 15, day 120 +/- 14 days; Visit 16, day 180 +/- 14 days; and Visit 17, day 365 +/- 14 days)

Additional analysis of the impact of study drug on metabolic outcomes (Section 5.4) will be determined at 1-, 3-, 6-, and 12-months following treatment including analysis of changes of these parameters from baseline.

Target Engagement, Mechanistic Outcomes and Exploratory Analysis

The primary time period for evaluation of target engagement and mechanistic outcomes will be accumulated data through visit #14.

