6.3 COVARIATES AND STRATIFICATION FACTORS

The potential influences of baseline patient characteristics such as age, gender, C-peptide level following a MMTT at study entry on the primary and secondary endpoints will be evaluated in a multivariate model to see whether they have an effect on the treatment vs. placebo comparison.

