8.2.3 MMTT ANALYSES

Acceleration of beta cell destruction due to immune activation is a potential risk, which will be monitored through $AUC_{0-2h,C-peptide,MMTT}$. The plasma C-peptide concentration-time curve from time 0 to 2 hours during MMTT obtained at the end-of dosing day 85 for the treatment and placebo arms will be compared for each cohort (N=3 placebo, and N=9 treated) and at the end of the study by cohort (i.e., pooling the placebo treated patients, N=12 placebo, N=9 treated in each cohort).

The MMTT analysis will be conducted on a transformed scale using the function log (1+ $AUC_{0-2h,C-peptide,MMTT}$). This provides better normal distributional behavior by the test statistic. The comparison between the two treatment arms will be based on a test of the difference between the means.

When an adjustment for covariates is desired, the comparison will be made using a Wald test of treatment effect in an ANCOVA model adjusting for gender, baseline age, and baseline.

The study has a 72%-87% power to detect a 50% or less treatment ratio when the coefficient of variation (CoV) ranges from 0.38 to 0.31. This is based upon historical data derived from recent onset patients (REF). Should the observed CoV be larger, there would be a corresponding reduction in power to detect a 50% treatment ratio or a corresponding decrease in the detectable treatment ratio to retain 80% or greater power. The power to detect a 50% or less treatment ratio at the end of the study (using the pooled placebo patients) is uniformly >90%.

Additionally, using a published methodology, the observed transformed AUC C-peptide can be compared visually with the expected AUC C-peptide calculated from TrialNet historical data from untreated recent onset patients.

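### The secondary endpoint is change in C-peptide AUC from baseline, but the SAP's stated test compares end-of-dosing levels, leaves baseline adjustment optional and names no model for the endpoint

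*SAP*

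**What the plan says.** The endpoint is a change. SAP 6.2 defines it as "Relative change in the area under the plasma C-peptide concentration-time curve from time 0 to 2 hours during MMTT from baseline" to visit 14, compared between groups, and protocol 8.2 agrees. Neither section names a test.

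The method is for a level. SAP 8.2.3 takes the end-of-dosing MMTT, transforms it to log(1+AUC), and compares arms within each cohort (3 placebo v 9 active) and again with placebo pooled (12 v 9): "The comparison between the two treatment arms will be based on a test of the difference between the means". Protocol 8.5 makes the same level comparison on a different scale, "The log-transformed area under the plasma C-peptide concentration-time curve".

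Baseline appears in three places, none of which designates the endpoint analysis:

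- SAP 8.2.3: "When an adjustment for covariates is desired, the comparison will be made using a Wald test of treatment effect in an ANCOVA model", whose covariates are listed as gender, age and an item given only as baseline. There is no rule for when adjustment is desired and no reference distribution for the Wald test.
- SAP 6.3: age, gender and entry C-peptide "will be evaluated in a multivariate model to see whether they have an effect on the treatment vs. placebo comparison".
- SAP 6.2 and protocol 8.3: additional change-from-baseline analyses of metabolic outcomes, with no model.

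On timing, SAP 6.2 adds: "The comparison will be blinded until the last patient has been followed for 12 months".

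**The concern.** An endpoint defined relative to baseline has as its plainly stated test one that ignores baseline. At least three analyses fit the text: the unadjusted level, the ANCOVA, and the relative change itself. With 3 placebo participants in a cohort these can disagree by chance alone. Blinding delays the choice but does not make it: either test complies with the SAP, so picking one after unblinding would not count as a deviation.

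The pooled comparison is more exposed. Nine of its 12 placebo participants come from cohorts other than the active group's, and cohorts enroll in sequence (protocol 4.8: "If approved by both, randomization of the next cohort will proceed"). Randomization does not fully protect baseline balance there.

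The scale is a further gap. A difference on log(1+AUC) depends on the unit of AUC and does not directly give the treatment ratio used in the power statement.

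At stake is how reliably the trial reports accelerated beta-cell loss, which both documents name as a potential risk.

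**Working it through.** **Inputs from the documents.** Treatment ratio 0.50; CoV 0.38 to 0.31; 3 v 9 within a cohort and 12 v 9 pooled; stated power 72% to 87%, and above 90% pooled (protocol 8.5, SAP 8.2.3).

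**Assumed.** Two-sided 5%, which is not stated but reproduces the figures. The correlation ρ between baseline and month-3 log AUC is not in the documents, so a range is shown.

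**1. The plan's own power.** Log SD = √ln(1+CoV²) = 0.367 (CoV 0.38) or 0.303 (CoV 0.31). Noncentrality = ln 2 / [SD·√(1/n₁+1/n₂)], df = n₁+n₂−2.

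- 3 v 9, CoV 0.38: 0.693/(0.367×0.667) = 2.83 on 10 df, power 72.3%. At CoV 0.31: 87.1%.
- 12 v 9: 98.2% and 99.8%.

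These match the stated figures with no baseline term, so the stated power is consistent with the unadjusted level test. A test of log change has SD·√(2(1−ρ)), which equals the level test only at ρ = 0.5. For 3 v 9 at CoV 0.38 its power for a halving is 57.9%, 72.3% and 90.8% at ρ = 0.3, 0.5 and 0.7.

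**2. Power with baseline AUC as the one covariate.** By formula, SD becomes SD·√(1−ρ²) with one df fewer. Simulation used 40,000 trials per cell with bivariate normal log AUC. CoV is 0.38; a 30% loss is a ratio of 0.70.

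| Comparison | Unadjusted | ρ=0.3 | 0.5 | 0.7 | 0.8 | 0.9 |
|---|---|---|---|---|---|---|
| 30% loss, 12 v 9, formula | 55% | 59% | 67% | 83% | 93% | >99% |
| 30% loss, 12 v 9, simulation | 55% | 56% | 65% | 81% | 92% | >99% |
| 30% loss, 3 v 9, simulation | 26% | 26% | 30% | 41% | 54% | 80% |
| Halving, 3 v 9, simulation | 72% | 71% | 79% | 91% | 97% | >99% |

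At CoV 0.31, unadjusted power for a 30% loss at 12 v 9 is 72%. For a halving at 12 v 9 there is almost nothing to gain, since power is already 98%.

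**3. Open choice of test.** In 60,000 null trials per cell (ρ 0.3 to 0.9, sex assumed 50:50), the smaller of the p-values from the unadjusted t-test and the three-covariate ANCOVA (t reference) falls below 5% in 7.2–9.5% of trials at 12 v 9 and 7.7–9.6% at 3 v 9.

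**4. Wald reference.** The three-covariate ANCOVA has five coefficients, so error df are 21−5 = 16 and 12−5 = 7. If the Wald statistic were referred to the normal, its size would be 2·P(t>1.96) = 6.8% on 16 df and 9.1% on 7 df.

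**5. Drift between cohorts in the pooled comparison.** Let cohort mean log baseline vary with SD τ (assumed) and carry to month 3 with slope ρ; 60,000 null trials.

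- τ = 0.2: unadjusted false positives are 7.5%, 9.7%, 11.4% and 12.3% at ρ = 0.5, 0.7, 0.8 and 0.9, against about 5% adjusted.
- τ = 0.1: unadjusted 5.7–7.1%.
- τ = 0.2 with drift carried over fully (slope 1): 14% unadjusted, 5.3–7.0% adjusted.

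**6. Scale.** When AUC m is halved, the ratio of (1+AUC) is (1+m/2)/(1+m). For an assumed m = 0.5 pmol/mL this is 1.25/1.5 = 0.83; for an assumed m = 60 pmol/mL × min it is 31/61 = 0.51. The same halving gives two different numbers, although the scale does not harm power.

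**The case against.** The strongest reply is that an adjusted analysis is already planned. SAP 6.3 commits to evaluating entry C-peptide in a model for the secondary endpoint, and the ANCOVA in 8.2.3 lists matching factors, so baseline C-peptide is the natural reading of its last covariate. That is fair, but 6.3 only asks whether covariates affect the comparison. It does not say which result is the endpoint result.

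Second, under randomization log level and log change target the same ratio. This stands for the within-cohort comparison, where the loss is precision and analyst choice.

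Third, the magnitudes are assumed. The plan powers only for a halving; the 30% loss, the correlation and the drift are not in the documents. A τ of 0.2 is more than half the individual log SD, and every cohort has the same entry criteria. The documents also do not say whether the CoV describes raw or already adjusted variation. If adjusted, step 2 counts the gain twice, and dropping one df in step 1 still gives 71.3% and 86.2%. These points limit how firmly the sizes can be stated; they do not supply a designated model.

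Fourth, nobody plans to report the smaller p-value, and protocol 8.1 requires a final SAP before unblinding. A final SAP that permits both tests still leaves the choice open.

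Last, log(AUC) is undefined at zero, and such participants would be the worst cases of the risk being monitored. This stands, and the fix must cover it.

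**Conclusion.** The point holds and should be fixed before unblinding. The wording gap is certain: the endpoint uses baseline, the stated test does not, and no model is designated. The sizes are conditional. At CoV 0.38 and two-sided 5%, adjustment would raise pooled power for a 30% loss from 55% to between 59% and 93% for ρ from 0.3 to 0.8 (56% to 92% in simulation), with a negligible gain for a halving. Free choice between the two tests could raise the false-positive rate to 7–10%. Cohort drift could raise the unadjusted pooled rate to 7.5–12.3% if τ were 0.2, or 5.7–7.1% if it were 0.1. The descriptive primary endpoint and the dose-escalation decisions are unaffected.

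**What to change.** In SAP 8.2.3, before unblinding:

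1. Designate as the analysis of the secondary endpoint an ANCOVA of log(AUC at visit 14) on treatment, with log(baseline AUC) as the one mandatory covariate and a t reference. Use it for both the per-cohort and the pooled-placebo comparisons.
2. Report the exponentiated treatment coefficient with a 95% CI as the ratio of relative changes.
3. Delete the clause that makes adjustment optional. Keep the unadjusted test, and any model adding gender and age, as sensitivity analyses.
4. Reconcile log(AUC) in protocol 8.5 with log(1+AUC) in SAP 8.2.3. With log(AUC), add a rule for zero or unquantifiable C-peptide. If log(1+AUC) is kept, apply it to baseline too, state the unit, and do not report the difference as a treatment ratio.

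The cost is SAP wording. The data exist: protocol 5.4 schedules the "2-hour MMTT at screening and at 1, 3, 6, and 12 months after initial treatment dose", and the screening test is needed for eligibility. The model spends one error degree of freedom. At 3 v 9 with ρ as low as 0.3, that costs about one point of power for a halving (71.5% v 72.8% in simulation). A participant whose screening AUC counts as missing under SAP 7.2 would drop out of the model.
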